#### 7.2.4.8 Time to first hospitalization (all cause)

If the subject was hospitalized, then the hospitalization will be defined as all cause. The time to first hospitalization (all cause) in weeks will be derived as (date of first hospitalization – date of randomization +1)/7.

If a patient does not require hospitalization on or prior to Day 379, the same censoring rules will apply as in Section 7.2.3.3.

If there are fewer than 15 hospitalizations (all cause) then statistical analysis will not be performed, and only frequencies of hospitalizations by treatment group will be provided. Otherwise, the same analysis (Cox proportional hazards modelling) as detailed in Section 7.2.3.3 will be performed.

#### 7.2.4.9 Time to respiratory-related death

Respiratory related causes will be defined as in Section 7.2.3.3. The time to death due to respiratory related causes, in weeks, will be derived as (date of respiratory-related death – date of randomization +1)/7.

If a patient does not die due to respiratory related causes on or prior to Day 379, the same censoring rules will apply as in Section 7.2.3.3.

Cox proportional hazards modelling, as detailed in Section 7.2.3.3, will be performed.

	Plus-Project Statistical Analysis Plan	
	Protocol Number: GALACTIC-1	Version: 1

7.2.4.10 Change in FVC expressed in mL over 52 weeks for subjects who have never been treated with pirfenidone or nintedanib

The same data source and analyses (random coefficients regression model) as detailed in Section 7.2.1 will be used. Statistical analysis will be performed for the Primary Population and descriptive analyses only for the SoC2 / Monotherapy Population.

**7.2.5 Exploratory Endpoints**

Unless otherwise stated, exploratory endpoints will be summarized in the Primary Population only, using the mITT analysis set.

7.2.5.1 Biomarkers

Biomarker results will be provided by the central laboratory in standard units. The results, change from baseline and percentage change from baseline (for post baseline assessments) will be summarized by visit.

Correlation analyses assessing the relationship between Biomarker results and efficacy/safety endpoints may be performed.

7.2.5.2 Time to initiation of pirfenidone or nintedanib treatment for SoC2 subjects recruited to the original study design

Only the SoC2 / Monotherapy Population will be used, with only subjects recruited to the original study design (pre-Protocol V6.0).

The time to initiation of pirfenidone or nintedanib treatment will be derived from the 'Pirfenidone/Nintedanib Usage' eCRF. The time to initiation of pirfenidone or nintedanib treatment in weeks will be derived as (date of first initiation of pirfenidone or nintedanib treatment – date of randomization +1)/7.

Time to initiation will be summarized descriptively by treatment.

7.2.5.3 Time to termination of pirfenidone or nintedanib treatment

Summaries of time to termination of pirfenidone or nintedanib treatment will be conducted only for the SoC1 / Combination Population.

The time to termination of pirfenidone or nintedanib treatment will be derived from the 'Pirfenidone/Nintedanib Usage' eCRF. The time to termination of pirfenidone or nintedanib treatment in weeks will be derived as (date of last dose of pirfenidone or nintedanib

	Plus-Project Statistical Analysis Plan	
	Protocol Number: GALACTIC-1	Version: 1

treatment – date of randomization +1)/7.

Time to termination of pirfenidone or nintedanib treatment in the SoC1 / Combination Population will be summarized descriptively.

#### 7.2.5.4 Pharmacogenetics

Pharmacogenetic results will be provided by the central laboratory. The results will be summarized by treatment group.

The primary and key secondary endpoint subgroup analyses may be repeated including a post-hoc classification of pharmacogenetic results as a subgroup.

Additional analyses assessing the relationship between Pharmacogenetic results versus safety endpoints may also be performed.

### **7.3 Safety**

Safety evaluations will be performed on the Safety Set, unless otherwise specified. Missing assessments will not be imputed unless stated otherwise. All analyses will be conducted on the Primary Population. Key safety will also be summarized for the SoC1 / Combination and SoC2 / Monotherapy Populations, as detailed in the individual sections.

#### **7.3.1 Exposure and Treatment Compliance**

Details of exposure and treatment compliance will be summarized for the mITT Analysis Set, as well as for the Safety Analysis Set. In addition, for the Primary Population only, exposure and compliance will be summarized in the PP Analysis Set.

Date of first dose of study treatment will be derived as the earliest date of drug dispense from the ‘Treatment Compliance’ eCRF forms.

Extent of exposure to GB0139 (mg) or Placebo will be calculated based on information from the ‘Treatment Compliance’ eCRF forms. The number of capsules used will be derived as the number of GB0139 capsules dispensed minus the number of unused GB0139 capsules returned during the study. The number of GB0139 capsules used and the dose of GB0139 in the capsules known to have been dispensed will be used to derive the extent of exposure (mg) to GB0139.

	Plus-Project Statistical Analysis Plan	
	Protocol Number: GALACTIC-1	Version: 1

The duration of exposure to GB0139 in days will be calculated as the date of last dose recorded in the 'Disposition Study Completion' eCRF minus the date of first dispensing of GB0139 + 1.

The duration of exposure to GB0139 will be summarized both as a continuous variable and categorically, with categories 0-13 weeks, >13 weeks – 26 weeks, >26 weeks=39 weeks, >39 weeks – 52 weeks, > 52 weeks.

The extent of exposure (mg) will be summarized as a continuous variable by treatment group.

The extent (mg) and duration of exposure (days) between each dispensing and returning of study drug will be presented in the listings but will not be summarized.

The duration of exposure to nintedanib or pirfenidone during treatment with study drug will be derived based on the start and stop dates of nintedanib and pirfenidone from the 'Pirfenidone/Nintedanib Usage' eCRF and the first and last date of study drug.

The expected treatment exposure (capsules) will be derived using the treatment duration with study drug multiplied by 2 (the planned daily number of capsules).

Treatment compliance based on dispensing data will be derived as 100 x treatment exposure (capsules) / expected treatment exposure for duration of study treatment through study treatment discontinuation (capsules).

The treatment exposure to study drug (capsules), treatment duration with study drug (days) and treatment compliance (continuous and grouped as < 80%, 80% to 120%, > 120%) will be summarized.

The treatment exposure to study drug (capsules), treatment duration with study drug (days) and treatment compliance between each dispensing and returning of study drug will be presented in the listings but will not be summarized.

Summaries will be repeated in the SoC1 / Combination and SoC2 /Monotherapy Populations. In the SoC1 / Combination Population treatment compliance will be repeated by baseline SoC treatment at baseline (Nintedanib vs Pirfenidone vs Pirfenidone and Nintedanib).

### **7.3.2 Adverse Events**

Adverse events (AEs) from the 'Adverse Events' eCRF will be coded for summarization using the most recent upversioned MedDRA coding as specified in the DMP. In the event that no

	Plus-Project Statistical Analysis Plan	
	Protocol Number: GALACTIC-1	Version: 1

coding information is available for a specific AE, the AE will be presented as an “Uncoded” in summary tables.

A Treatment Emergent AE (TEAE) is defined as any protocol defined AE (collected as a unique record from the AE eCRF page) with an onset between the date of first dispensing of study drug (from the ‘Treatment Compliance’ eCRF forms) and date of last dose recorded + 14 days inclusive (date of last dose from the ‘Disposition Study Completion’ eCRF). If the date of onset is the same as the date of first dispensing of study drug, then the recorded start of event relative to first dose from the eCRF (before/after) will be used to classify the AE as either a TEAE (after) or a non-TEAE (before).

Missing and/or incomplete dates/times for AEs will not be imputed. For partial/missing dates:

- If the start or stop month/year (if day is missing) or year (if day and month are missing) of the AE is prior to the respective month/year or year of the first dose of study drug, then the AE will be classed as a Non-TEAE.
- If the start month/year (if day is missing) or year (if day and month are missing) of the AE is after the respective month/year or year of the last dose of study drug + 30 days, then the AE will be classed as a Non-TEAE.
- Otherwise, the AE will be classed as a TEAE.

For TEAE summaries presenting the incidence frequency and percentage, the number of actual unique TEAEs (meeting each criteria) will also be presented. For incidence summaries, a subject with multiple TEAEs will contribute only once to the count for a given summary and the maximum severity and relationship will always be used. The number of unique TEAEs will always be presented as per the severity and relationship for the unique TEAEs. Missing relationship will be considered related to study drug and missing severity will be considered severe.

The number and percentage of subjects reporting at least one of the following will be summarized:

- TEAE
- TEAE by maximum severity (overall and within related TEAEs)
- TEAE by maximum relationship to study drug (overall and within serious TEAEs)
- Serious TEAE
- TEAE leading to treatment discontinuation
- TEAE leading to death
- All deaths (Note: time to death is limited to a follow-up period of Day 379)

	Plus-Project Statistical Analysis Plan	
	Protocol Number: GALACTIC-1	Version: 1

Further summaries by SOC and PT will be produced for all TEAEs, TEAEs by SoC, PT and maximum severity, treatment related TEAEs, serious TEAEs, TEAEs leading to treatment discontinuation and TEAEs leading to death. These will be presented by SOC and PT, sorted by decreasing frequency overall and then alphabetically. An additional summary all AEs post follow-up (i.e. post treatment end date + 14) will be produced by SOC and PT.

Additional summaries of all TEAEs and of serious TEAEs by PT only, sorted by decreasing frequency overall, will be presented.

Summaries of COVID related (per eCRF) TEAEs and serious COVID related TEAEs will also be produced. In addition, summaries of TEAEs and Serious TEAEs related to IPF exacerbations (i.e. those events marked on the eCRF as related to IPF exacerbation) will be provided.

Serious TEAEs and TEAEs leading to discontinuation of study drug will be presented separately for the SoC1 / Combination and SoC2 / Monotherapy Populations.

Additionally, the incidence of by time period (0 - 13 weeks, >13 weeks – 26 weeks, >26 weeks - 39 weeks, >39 weeks – 52 weeks, ≥ 52 weeks) will be presented. The presentation will include all TEAEs, serious TEAEs, TEAEs leading to treatment discontinuation, and TEAEs leading to death. The denominator for each period will be the number of subjects on treatment at the beginning of that time period. This summary will be repeated for the SoC1 / Combination and SoC2 / Monotherapy Populations.

Each TEAE event rate (per 100 patient years) will also be summarised by preferred term within each system organ class. For each preferred term, the event rate will be presented and will be defined as the number of patients with that AE divided by the sum of the duration from the start of treatment to 14 days after the last treatment dose (for patients without the event) and the time to the AE (for patients with the event) in each group multiplied by 100. This will also be repeated for serious TEAEs.

Risk differences for proportion of subjects with the following TEAEs (with associated 95% confidence intervals) comparing GB0139 groups to Placebo will be estimated:-

- TEAE
- TEAE by maximum severity (overall and within related TEAEs)
- TEAE by maximum relationship to study drug (overall and within serious TEAEs)
- Serious TEAE
- TEAE leading to treatment discontinuation
- TEAE leading to death

Separate subject listings will be provided for AEs leading to death (including a flag for TEAEs), Serious TEAEs and TEAEs leading to treatment discontinuation. A listing of all deaths will also be produced.

	Plus-Project Statistical Analysis Plan	
	Protocol Number: GALACTIC-1	Version: 1

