11.1.2 Treatment Emergent Adverse Event

A treatment emergent adverse event (TEAE) is any untoward medical occurrence that emerges during treatment, having been absent pre-treatment or worsens relative to the pre-treatment state.

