14.5.2 Safety Analysis

The primary assessment of benefit-risk of GB0139 3 mg compared to Plc will be based on efficacy and safety data over 52 weeks. All safety assessments described below will focus on

data collected within the first 52 weeks of the study. In addition, selected safety analyses will be repeated to include data collected beyond 52 weeks; further details will be specified in the SAP.

All treated subjects will be included in the safety analysis. The primary safety assessment will be based on the participants who received 3mg or placebo as study treatments. A separate safety assessment will be made for the participants who received study treatment in combination of nintedanib or pirfenadone. The particular tables and figures to be split in this way will be specified in the SAP. In general, safety analyses will be descriptive in nature. No hypothesis testing is planned.

Kaplan-Meier plots will be produced for the time to premature treatment discontinuation. Statistical analysis and reporting of adverse events will concentrate on treatment-emergent adverse events. All adverse events occurring between start of treatment and end of the residual effect period will be considered 'treatment-emergent'. The residual effect period is defined as the 28 days after the date of the last dose of trial medication. Adverse events that start before first drug intake and deteriorate under treatment will also be considered 'treatment-emergent'. Frequency, severity, and causal relationship of adverse events will be tabulated by system organ class and preferred term after coding according to the current version of MedDRA.

Laboratory data will be analysed both quantitatively as well as qualitatively. The latter will be done via comparison of laboratory data to their reference ranges. Values outside the reference range as well as values defined as clinically relevant will be highlighted in the listings. Treatment groups will be compared descriptively with regard to distribution parameters as well as with regard to frequency and percentage of subjects with abnormal values or clinically relevant abnormal values.

Vital signs, physical examinations, or other safety-relevant data observed at screening, baseline, during the course of the treatment and at the end-of-treatment evaluation will be assessed with regard to possible changes compared to findings before start of treatment.

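### The SAP's treatment-emergent window (14 days for full dates, 30 for partial dates) departs from the protocol's 28 days without being declared, and its onset-only definition omits the protocol's worsening rule

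*SAP*

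**What the plan says.** **Protocol.** Section 14.5.2 treats events from start of treatment to the end of a residual effect period as treatment-emergent: "The residual effect period is defined as the 28 days after the date of the last dose of trial medication". It adds a worsening rule: "Adverse events that start before first drug intake and deteriorate under treatment will also be considered" treatment-emergent. Section 11.1.2 agrees, defining a TEAE as an event "having been absent pre-treatment or worsens relative to the pre-treatment state".

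**SAP 7.3.2, full dates.** A TEAE is "any protocol defined AE (collected as a unique record from the AE eCRF page) with an onset between" first dispensing and "date of last dose recorded + 14 days inclusive". Onset is the only timing criterion, and there is no worsening clause.

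**SAP 7.3.2, partial dates.** If the day (or day and month) is missing, the late cut-off compares month and year (or year alone) with those of the "last dose of study drug + 30 days, then the AE will be classed as a Non-TEAE". Anything not ruled out counts as a TEAE.

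**SAP 7.3.2, rates and later events.** Person-time per 100 patient-years, for subjects without the event, is "the sum of the duration from the start of treatment to 14 days after the last treatment dose". Events after treatment end + 14 days go to a separate summary by system organ class and preferred term.

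**SAP 7.2.4.6.** The AE/SAE secondary endpoint is restricted to TEAEs starting before Day 379.

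**SAP Section 9.** The listed changes from the protocol include one as small as Wald in place of likelihood-ratio tests. Neither the window nor the worsening rule is listed.

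**The concern.** One definition has three lengths across the two documents, two of them within a single SAP section. Followed literally, the SAP classifies an event by how completely its date was recorded, and the less complete record gets the wider window.

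The definition feeds most of the comparative safety output: serious TEAEs, TEAEs leading to death, TEAEs leading to discontinuation, the risk differences with 95% intervals, the rates per 100 patient-years and a listed secondary endpoint. Protocol 11.3 asks for AEs and SAEs to be reported for 30 days after last dose, so the plan would leave out of these results events it intends to collect.

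The subjects most exposed are those who stop study drug early and remain under observation, as Protocol 6.2 and 10.5 allow. Some of them stop because they are deteriorating, so days 15–28 are a period in which serious events are plausible.

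**Working it through.** The plan gives no calculated figure on this point. The 28, 14 and 30 days are definitions, so the check is a comparison of texts plus day arithmetic.

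**1. The windows side by side**

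| Use | Source | End of window |
|---|---|---|
| TEAE definition | Protocol 14.5.2 | last dose + 28 days |
| TEAE, full date | SAP 7.3.2 | last dose + 14 days |
| TEAE, partial date | SAP 7.3.2 | month or year of last dose + 30 days |
| Rate denominator | SAP 7.3.2 | last dose + 14 days |
| Post-treatment AE table | SAP 7.3.2 | starts after treatment end + 14 days |

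**2. One event, two classifications.** Take a last dose on 15 March. The SAP full-date window ends on 29 March (+14), the protocol window on 12 April (+28), and the partial-date anchor is 14 April (+30). A serious AE dated 5 April (day 21) is a TEAE under the protocol and not under the SAP. Recorded only as *April*, it is a TEAE under the SAP, because April is not after the anchor's month.

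**3. Reach of the partial-date rule.** With the day missing, the latest true onset still counted is the last day of the month containing last dose + 30. For a 15 March last dose that is 30 April, day 46. Over all last-dose dates in a year it runs from day 30 (anchor on the last day of a month) to day 60 (anchor on the first of a 31-day month: 30 + 30). The gap to the 14-day rule is therefore 16 to 46 days, depending on the calendar. With the month also missing, only years are compared and the reach can be longer.

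**4. Share of the protocol's at-risk window removed.** For T days on drug, share = 14 / (T + 28).

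| Days on drug | Calculation | Share |
|---|---|---|
| 365 | 14/393 | 3.6% |
| 182 | 14/210 | 6.7% |
| 91 | 14/119 | 11.8% |
| 28 | 14/56 | 25% |

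**5. Expected number of events.** The documents give no AE rate, so this is an assumption with a range. With the planned 141 subjects, a constant rate r per patient-year and everyone observed through day 28, expected events on days 15–28 = 141 × r × 14/365.25.

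- r = 0.1: 0.5 events
- r = 0.25: 1.4
- r = 0.5: 2.7
- r = 1.0: 5.4

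These run high to the extent that subjects are not observed to day 28.

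**6. Secondary endpoint.** An onset on day 15 after a last dose on study day L falls before Day 379 only if L + 15 ≤ 378, so L ≤ 363. The 14-day rule therefore changes this endpoint only for subjects whose last dose is on or before Day 363. For later last doses the Day 379 limit already excludes the same events.

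**7. Worsening.** The SAP counts protocol-defined AEs, and Protocol 11.1.3 includes a previous condition that has increased in severity or frequency since study drug. Worsening entered as a new record with a post-dose onset would count. An event with a pre-dose onset that deteriorates within the same record would not, although Protocol 14.5.2 counts it. Neither document says how worsening is to be recorded.

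**The case against.** The strongest defence is that the events are reported and the worst are compared between arms by other routes.

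- **Deaths.** SAP 7.3.2 summarises and lists all deaths, and its listing of AEs leading to death flags which are TEAEs. SAP 7.2.3.4 compares time to all-cause death to Day 379 whatever the event count. A death after day 14 is still a TEAE leading to death if the causal AE began by day 14.
- **Hospitalisations.** SAP 7.2.3.3, 7.2.4.7 and 7.2.4.8 analyse first hospitalisations to Day 379 without reference to last dose, with frequencies by arm if there are fewer than 15 events.
- **Later AEs.** These are tabulated by class and term, with treatment columns under SAP 5.4.

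All of this stands. A reader might infer that late serious and fatal events disappear or escape any comparison between arms; the documents do not support that. What is missing is narrower: the post-treatment table has no planned split by seriousness, no risk difference and no rate.

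A second defence is that 14 days fits the follow-up. The schedule notes collect AEs only to the phone call, which Protocol 10.3.4 places 7 to 14 days after the last visit. A flat 28-day denominator could then add unobserved time for completers. This is a fair warning about the remedy. But Protocol 11.3 says 30 days, the SAP gives no reason for 14, and the fit does not explain the 30-day partial-date rule.

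Third, classing uncertain dates as treatment-emergent is a common conservative default. True: that rule adds events and causes none of the loss. It is still anchored to a different window from the one it supplements.

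Finally, the SAP was written to protocol version 7.0 (28 January 2022), while the protocol reviewed refers to itself as 6.1_UK. The undeclared departure from 28 days is therefore likely but not confirmed. The 14-versus-30-day conflict inside the SAP does not depend on the version.

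**Conclusion.** The conflict is real and should be settled before database lock. Full-date events on days 15–28 leave the TEAE-based counts, risk differences and rates, and partly the AE/SAE endpoint, while partial-date versions of the same events can stay in. The effect is modest overall and concentrated in early stoppers: 3.6% of the at-risk window for a 365-day completer, 25% after 28 days on drug, and roughly 0.5 to 5.4 events in all under the assumed 0.1 to 1.0 events per patient-year. A few events could still matter for serious or fatal counts.

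The worsening omission is a separate gap. It concerns events that began before dosing and does not contribute to the late-event loss. It bites only if worsening stays in the pre-dose record, which the documents leave open.

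Three stronger readings should be avoided. The SAP does not halve the whole at-risk window; it halves only the post-dose tail. The full-date and partial-date rules do not differ by a fixed 16 days, which is the smallest gap with the day missing. And nothing shows that 14 days favours either arm or bears on the redesign: under Protocol 12.1 the DSMB's safety reviews focus on deaths, SAEs and AEs leading to withdrawal, with no mention of the treatment-emergent window.

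**What to change.** 1. Apply the protocol's 28-day window to full dates, partial dates and the start of the post-treatment AE table.
2. In the rate denominator, end person-time at the earlier of last dose + 28 days and the end of AE follow-up, so that unobserved time is not counted.
3. Add to SAP 7.3.2 that a pre-dose event worsening after first dose is treatment-emergent, and state how worsening is identified in the eCRF.
4. Reconcile the AE collection period: the schedule notes stop at the phone call, whereas Protocol 11.3 runs to 30 days after last dose.
5. Confirm that protocol version 7.0 carries the 28-day text.

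If 14 days is kept, declare it with a reason in SAP Section 9, align the partial-date rule to it, and repeat the serious and fatal TEAE tables and the risk differences on the 28-day window.

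The cost is SAP wording and minor programming. Counts of full-date events can only stay the same or rise. Rates may move either way, because numerator and person-time both grow.
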